# List of Abbreviations and Definition of Terms

Abbreviation	Definition
AE(s)	Adverse Event(s)
ANCOVA	Analysis of Covariance
ANOVA	Analysis of Variance
B&A	Balance and Assignment
CFR	Code of Federal Regulations
CRF(s)	Case Report Form(s)
DSMB	Data Safety Monitoring Board
FDA	Food and Drug Administration
GCF	Gingival Crevicular Fluid
GCP	Good Clinical Practices
GI	Gingivitis Index
IRB	Institutional Review Board
LS	Löe-Silness
SOP(s)	Standard Operating Procedure(s)
TEAE(s)	Treatment-Emergent Adverse Event(s)
TMF	Trial Master File

## 1. Background

Gingivitis is one of the most prevalent oral diseases, affecting a majority of dentate adults. Onset often begins in adolescence, and may persist throughout adulthood. Marginal gingival bleeding and redness represent common clinical signs. Dental plaque plays a prominent role in the development of gingivitis, with hormonal and other factors occasionally contributing to the onset or severity of gingival inflammation. Inadequate oral hygiene is recognized to contribute to plaque accumulation, and subsequent gingivitis. Gingivitis may be induced through voluntary or involuntary withdrawal of routine oral hygiene. Two-to-three weeks following cessation of toothbrushing, sufficient pathogenic plaque develops to manifest clinical gingivitis in otherwise healthy individuals. Both natural and induced gingivitis can be resolved with thorough oral hygiene (brushing and flossing), or routine dental prophylaxis.

Gingivitis may be assessed through various qualitative or quantitative methods. Clinical examinations may include assessment of marginal gingival color, and/or bleeding with or without superficial provocation of gingival tissues. Some methods combine marginal color and bleeding in a single non-linear clinical index, such as the Loe-Silness Gingivitis Index (GI). Assessments made be made at specific, representative sites or throughout the whole mouth. Other methods may assess color, bleeding severity, location or other factors. Given the subjective nature of the clinical assessment, examiner training and calibration may play a role in gingivitis measurement.

Irrespective of the method, there is considerable variation in the extent and severity of gingivitis. In one survey, gingivitis was common with US adults 18-65 exhibiting a mean of 19.4 gingival margin bleeding sites. Gingivitis and bleeding scores were highest on the mandibular anterior facial and lingual sites, and maxillary posterior facial sites, bilateral symmetry was evident, and proximal sites were most commonly affected. Oral hygiene was associated with gingival inflammation and bleeding, with individuals having higher reported frequency of brushing or flossing having significantly (p < 0.05) lower gingivitis and bleeding. For brushing, bleeding site means were 24.2 with QD brushing, compared to 17.5 with BID brushing. For flossing, bleeding was highest (27.1 sites) with no flossing and lowest (13.1 sites) with daily flossing. Gingivitis and bleeding were also significantly (p < 0.0001) related to subject perceived occurrence, frequency and severity of bleeding upon brushing, and gingivitis, bleeding and plaque scores were highly correlated (0.56-0.90).

Antimicrobial dentifrices and mouth rinses are recognized to play a role in the prevention and treatment of gingivitis. Various agents have been evaluated in randomized controlled clinical trials, with or without a preceding dental prophylaxis. Chlorhexidine, essential oils combinations, triclosan, cetylpyridinium chloride and other agents have been used in dentifrice or rinse formulations. Most of these actives target common aerobic microflora found in dental plaque. Effectiveness has been demonstrated in a few weeks or months, depending on the study model, population and others factors. Some agents, such as chlorhexidine, have been used in combination with other surgical or restorative dental care to reduce post-operative infection or inflammation. 13-15

Some research has focused on possible relationships between gingivitis and other diseases or conditions. For example, bleeding, which has long been identified as an important objective sign of gingival inflammation, is recognized as a risk factor for progressive periodontal disease and tooth loss.  Various health conditions have been implicated in the natural history of gingivitis. Along with plaque accumulation, other conditions like pregnancy, diabetes and immune deficiency have been shown to modulate the clinical expression of gingivitis.  Endogenous hormones are believed to play a role in plaque-associated gingivitis seen during puberty, menstruation and pregnancy.  The latter, "pregnancy gingivitis", has long been recognized as archetypical with respect to the clinical characterization of gingivitis. In clinical research, pregnant women are reported to experience approximately a 20% increase in plaque and gingivitis beginning in the late first trimester, which persists or worsens during pregnancy, and returns to baseline after delivery without other interventions. 

While pregnancy is recognized to contribute to clinical gingivitis, studies evaluating possible relationships between periodontal disease and pregnancy outcomes have equivocal results. Early research from a case control study among 124 pregnant women in North Carolina, USA identified periodontal disease extent and severity as a significant risk factor for preterm low infant birth weight. Several epidemiological and intervention studies followed, and meta-analysis of this complex research initially supported a role for periodontal treatment in reducing adverse pregnancy outcomes (birth weight or prematurity). Subsequently, a few high-quality clinical trials have specifically evaluated the role of intensive periodontal intervention (usually scaling and root planing) on pregnancy outcomes. These

included two large US multicenter intervention trials with a cumulative sample size exceeding 2500 women, wherein each study failed to show an impact of periodontal therapy on pregnancy outcomes. 22,23 Meta-analysis of the updated evidence reversed earlier findings, concluding that use of scaling and root planing had no significant effect on post-natal outcomes. 24 Study design, target population and choice of intervention and others have been subsequently identified as possible contributors to the results seen in these large multicenter controlled trials. 25

Despite its recognized prevalence in the target population, very few studies have explicitly evaluated the possible contribution of gingivitis to pregnancy outcomes. Evidence continues to implicate the oral microflora in adverse pregnancy outcomes, including species associated with gingivitis. For example, in animal models, *Fusobacterium nucleatum* has been shown to induce preterm birth in the pregnant mouse, while other research has demonstrated the feasibility of the translocation of oral bacteria collected from saliva to the placenta in the mouse. Provided in humans, oral bacteria have been implicated in two recent adverse pregnancy outcomes, including one report of fetal demise specifically attributed to *F. nucleatum*. Results from a recent study of women without periodontitis identified severe pregnancy-associated gingivitis on the anterior teeth due to the presence of certain oral pathogens, rather than changes in salivary hormones.

There is long-standing evidence that onset of pregnancy gingivitis may be very low in situations with exceptional plaque control. Daily oral hygiene is widely recognized as contributing to plaque control in the general adult population such as power brushes or floss, or antimicrobial-containing dentifrices or rinses to remove and/or inhibit dental plaque. Recent clinical research has shown considerable effects of combination approaches on plaque control in adults, wherein power brushes plus marketed antimicrobial dentifrices and rinses contributed to sustained reductions in overnight plaque accumulation that were comparable to levels measured immediately after a dental prophylaxis. 34,35

Two clinical trials were conducted to assess possible effects of improved daily oral hygiene on periodontal health in pregnancy. One study in Pennsylvania, USA evaluated use of a marketed 0.07% cetylpyridinium chloride rinse during pregnancy by a high-risk population with periodontitis relative to a non-randomized control group. The test rinse was selected, in part, because it was a marketed, alcoholfree formula that had been previously shown to yield significant antiplaque and antigingivits benefits similar to an alcohol-containing positive control rinse, with high compliance, favorable user acceptability. and minor side effects similar to with cosmetic mouthrinses. 12,36 Results demonstrated that subjects using the 0.07% cetylpyridinium chloride rinse averaged a 27-site mean reduction in periodontal bleeding (p<0.001) during treatment, while the control group remained largely unchanged. In addition, groups differed significantly (p<0.01) on birth outcomes, with the rinse group exhibiting lower incidence of preterm birth under 35 weeks, along with increased gestational age and birth weight relative to the control.37 Another study in Alabama, USA used the 0.07% cetylpyrdinium chloride rinse in combination with a 0.454% stannous fluoride dentiface, power brush, floss and oral hygiene instruction on pregnancy gingivitis relative to a historical control. The test paste was selected, in part, because it had previously demonstrated significant (p<0.05) reductions in gingivitis over an 8-week period when used with a power brush with or without floss. 38 Results demonstrated that subjects using combination oral hygiene therapy had significant reductions in gingivitis and plaque, with directional reductions in preterm birth under 37 weeks relative to the control. 39 Based on the results of these two initial pregnancy studies and related studies on the effects of oral hygiene combination therapy on oral health, a multicenter randomized controlled trial was designed to evaluate use of a marketed combination oral hygiene regimen on oral health during pregnancy.

## 2. Study Objective

The study will evaluate the effects of introduction of an advanced daily oral hygiene program by the late second trimester of pregnancy on gingivitis in pregnant women and subsequent maternity outcomes.

## 3. Overall Study Design and Plan

This is a multicenter randomized, controlled, single-blind, 2-treatment, parallel group clinical trial to assess gingivitis and maternity outcomes in pregnant women who undertake an advanced daily oral hygiene program. Up to 750 subjects will be enrolled to complete the study with a target population of approximately 600 evaluable subjects. Subjects will be adult female volunteers with moderate-to-severe gingivitis who are in the late first trimester or early-to-mid second trimester of pregnancy. Sufficient screening will be conducted to enroll approximately 300 subjects at each of two study centers. After informed consent and baseline measures are recorded, qualifying subjects will be randomly assigned in equal numbers to either 1) an advanced oral hygiene regimen consisting of marketed toothbrush. toothpaste, mouth rinse and floss plus oral hygiene education counseling, or 2) regular oral hygiene with an anticavity toothpaste, regular manual toothbrush and floss. Prenatal care will remain unchanged as part of study participation, following existing medical and institutional standards for treatment. Studyrelated evaluations will be scheduled, where possible, as part of routine prenatal visits, examinations will be conducted at Baseline before study product assignment, and monthly thereafter for 3 consecutive months of study product use. The primary outcome will be gingivitis and other clinical periodontal measures and samples will be collected. Adverse events will be collected from examination and interview. Oral hygiene and prenatal knowledge and practices will be assessed by survey at Baseline and Month 3. After Month 3, assigned oral hygiene products will be dispensed at prenatal visits or via home shipment through delivery. Maternity outcome data (gestational age) will be abstracted separately from medical records as a secondary variable, and other ancillary maternity data will be collected. An interim analysis of primary and secondary outcomes will be performed. The target population size and number of investigative sites may be adjusted as a result of the interim analysis. An independent Data Safety Monitoring Board will assess study design, conduct and outcomes at prescribed intervals using standard methods with respect to study integrity and continuance.

Table 1. Study Schedule by Procedure Type and Visit

PROCEDURE	BASELINE VISIT 1	MONTH 1 Visit 2	MONTH 2 Visit 3	Month 3 Visit 4	PRENATAL VISITS	MATERNITY OUTCOME	Post Study
Informed Consent	Х	III—IIESS I		/- = ->)	1400	- 0 (test) (test)	
Medical History Review	X	Х	Х	- X	10/2 11/2/01	697	
Concomitant Medications	Х	Х	Х	Х	1 3	ur Britis	
Demographics	Х	11-40	(100)	HEET		Lua Ross	
Inclusion/Exclusion Criteria	Х	- 10	nige -	100-2	ohe -	595	
Oral Hygiene Prenatal Care Survey	Х			Х			V
Continuance Criteria		Х	Х	X	9995	Писопре	
Oral Examination	Х	Х	Х	X	10 10 7		5
Optional Intraoral Photographs	Х	Х	Х	Х	- 144		
Gingivitis Examination	Х	X	Х	X	попира	me/iman	
Pocket Depth Examination	Х	Х	Х	Х	Kir vilo	31 =1	
Gingival Crevicular Sample Collection	X*	1111	HULLING OF THE	X*	38101	1990-021111111	
Oral Bacterial Sample Collection	X*			X*	10.311		SE.
Blood Sample Collection	X*		J211	X*	100	HESSAH (D)	
Product Distribution	Х	Х	Х	Х	1811	AUSHI II	7
Oral Hygiene Instruction and Supervised Use	х		oca mui minagii ĝ	IMPERIOR		ess pour mou hom	
General Comments	Х	Х	Х	Х		Х	
Adverse Events	X	Х	X	Х		Х	65
Subject Accountability	="1 TE	n un		100111	1 13111111	Х	82
Maternity Data from Medical Records	ullent vii	i finyla	DC E/1 II	10TH 16TH		Х	150
Optional Dental Prophylaxis		17(1(4)	All =s	12 41	ê	B 2850 B	X
Complementary Package Distribution	i	100					_ X

\*Samples will be stored and may be analyzed after primary and secondary study outcomes have been calculated. Sample analysis will be described elsewhere.

## Baseline Visit 1

Subjects will be asked to read and sign duplicate copies of the informed consent form which will be witnessed by site staff. Subjects will be given one signed copy of the informed consent form and the other signed copy will be maintained as site source documentation. Personal medical history information will be reviewed and retained as site source documentation; concomitant medications, height and weight will be recorded in the study database. Demographic information and entrance criteria will be assessed. Subjects will complete a survey on oral hygiene and prenatal knowledge and practices. A comprehensive oral examination will then be conducted to evaluate the oral and perioral region, including hard and soft tissues. Optionally, intraoral photographs may be taken. A trained and calibrated dentist will measure gingivitis and periodontal pocket depth. Gingival crevicular fluid samples and bacterial samples will be collected at two sites; sample collection sites will be recorded. Blood will be collected by venipuncture. Each sample will be stored for potential subsequent analysis. General comments and adverse events, if applicable, will be recorded.

Subjects will be randomly assigned to either the control group or the regimen group. The B&A computer program will assign a kit box number to a subject upon entry of the subject's stratification data. The subject number and kit box number will be recorded on forms provided by the Sponsor and/or suitable forms provided by the site. The kit box number assignment will be maintained and used for subsequent study product dispensing. Subjects will be given study products, instructed on product use and the first study product use will be supervised. All subjects will receive customary oral hygiene instruction, and in addition, subjects assigned to the regimen will receive counseling on oral hygiene, including an educational DVD on oral hygiene for personal use. All clinical examinations and interviews will be conducted by study personnel that are blind to treatment assignment, and uninvolved with oral hygiene education or product use training. The examiner will be in an area separate from randomization, product distribution, oral hygiene instruction and supervised use.

## Month 1 Visit 2

Continuance criteria will be assessed. Personal medical history information will be reviewed and updated and maintained as site source documentation. Concomitant medications and weight will be recorded in the study database. A comprehensive oral examination will then be conducted to evaluate the oral and perioral region, including hard and soft tissues. Optionally, intraoral photographs may be taken. A trained and calibrated dentist will measure gingivitis and periodontal pocket depth. Subjects will be given additional study products according to the kit box number assigned at the Baseline Visit. General comments and adverse events, if applicable, will be recorded.

## Month 2 Visit 3

Continuance criteria will be assessed. Personal medical history information will be reviewed and updated and maintained as site source documentation. Concomitant medications and weight will be recorded in the study database. A comprehensive oral examination will then be conducted to evaluate the oral and perioral region, including hard and soft tissues. Optionally, intraoral photographs may be taken. A trained and calibrated dentist will measure gingivitis and periodontal pocket depth. Subjects will be given additional study products according to the kit box number assigned at the Baseline Visit. General comments and adverse events, if applicable, will be recorded.

## Month 3 Visit 4

Continuance criteria will be assessed. Personal medical history information will be reviewed and updated and maintained as site source documentation. Concomitant medications and weight will be recorded in the study database. Subjects will complete a survey on oral hygiene and prenatal knowledge and practices. A comprehensive oral examination will then be conducted to evaluate the oral and perioral region, including hard and soft tissues. Optionally, intraoral photographs may be taken. A trained and calibrated dentist will measure gingivitis and periodontal pocket depth. Gingival crevicular fluid samples and bacterial samples will be collected at the same two sites sampled at Baseline; sample collection sites will be recorded. Blood will be collected by venipuncture. Each sample will be stored for subsequent analysis. General comments and adverse events, if applicable, will be recorded.

Subjects will be given an additional supply of study products according to the kit box number assigned at the Baseline Visit. Subjects assigned to the regimen will view an educational DVD on oral hygiene, and study product usage instructions will be reviewed. All clinical examinations and interviews will be conducted by study personnel that are blind to treatment assignment, and uninvolved with oral hygiene

education or product use training. The examiner will be in an area separate from product distribution, oral hygiene instruction and supervised use.

Used study products will not be returned to the clinical site; all study products are marketed oral hygiene products.

## General Comments and Adverse Event Recording

General comments and AEs may be recorded at any time during the study. Any Treatment-Emergent Adverse Event (TEAE) that remains unresolved by study end should be followed up until resolution by the Principal Investigator and resolution should be documented as source documentation. If a subject is unreachable to determine whether the TEAE has been resolved, the attempts to contact the subject should be documented as source documentation.

## Maternity Outcome (Record Review)

Maternity outcome data (plus ancillary variables such as birth weight) will be abstracted separately from medical records by trained personnel using standard methods. Maternal weight prior to delivery will be recorded. All maternity outcome data (including possible adverse events) will be collected from records by trained and qualified personnel who are blind to treatment assignment. A subject accountability form will be completed and subjects will be dismissed from the study. A subject accountability form will also be completed for subjects who drop out of the study prior to its completion.

## Optional Post-Study Dental Prophylaxis

Subjects that have been randomized and received study products and complete the Month 3 Visit or have been dropped due to the recommendation of the Principal Investigator (i.e. have a disease or condition that in the opinion of the investigator could interfere with the safe completion of the study) will be offered a complimentary dental prophylaxis after delivery.

## Post-Study Complementary Package

After completion of participation subjects that completed all study visits and had a live birth will be provided a complementary package containing marketed baby care products and replacement Oral-B® Precision Clean brush heads. In addition to the aforementioned products, subjects in the control group will receive an Oral-B® ProfessionalCare Series 1000 powered toothbrush with the Oral-B® Precision Clean brush head in the complementary package. Complementary packages will be identically sized and labeled except for a unique number used for assignment; complementary packages will be distributed according to the kit box number assigned at the Baseline Visit. Subjects that completed all study visits without a live birth will be provided a complementary gift card or equivalent compensation.

## 4. Inclusion Criteria

In order to be included in the study, each subject must:

- provide written informed consent prior to participation and be given a signed copy of the informed consent form;
- be at least the age of legal consent;
- be between 8 and 24 weeks of pregnancy;
- have at least 20 natural teeth:
- have moderate-to-severe gingivitis during pregnancy, including at least 30 intraoral sites with evidence of marginal gingival bleeding.

#### 5. Exclusion Criteria

Subjects are excluded from study participation where there is:

- evidence of multiple gestations;
- history of HIV infection, AIDS, autoimmune disease, or diabetes other than gestational diabetes;
- indication for use of antibiotic pre-medication prior to dental procedures;
- systemic corticosteroid or immunosuppressive therapy within 1 month of Baseline;
- severe periodontal disease, rampant untreated dental caries, or other oral conditions that necessitate immediate dental care;
- ongoing dental care that in the opinion of the investigator could impact study participation;
- a history of allergies or hypersensitivity to mouth rinse products containing CPC;
- any disease or condition that in the opinion of the investigator could interfere with the safe completion of the study;
- randomization to a treatment in study 2011001 during a prior pregnancy.

## 6. Continuance Criteria

Subjects may be excluded from the study or the analysis due to:

- non-compliance with study procedures;
- use of any non-study oral hygiene products;
- antibiotic, systemic corticosteroid or immunosuppressive therapy;
- dental prophylaxis or periodontal therapy;
- any disease or condition that in the opinion of the investigator could interfere with the safe completion of the study;
- urgent dental treatment that might impact study participation;
- elective termination of pregnancy.

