## Maternity Variables

For each subject, pertinent medical records are reviewed after delivery to determine maternity outcomes relating to gestational age. Neonate birth weight and Apgar score will also be recorded as ancillary variables.

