#### 2011001

If, for any reason, the subject does not complete the study, an explanation will be entered on the Subject Accountability CRF. All data gathered on the subject prior to discontinuation will be made available to the Sponsor.

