5.5 Rules and Conventions for Analyses

All data will be checked for accuracy, completeness, and compliance with the study protocol prior to breaking the treatment blind. The statistical analyses are the responsibility of the Sponsor's Department of Global Statistics and Data Management Department. In addition, a statistical analysis plan will be completed by the Sponsor prior to breaking the treatment blind. All statistical analyses will be performed using SAS®.

There are 2 evaluable populations, one for Birth outcomes and one for Gingivitis outcomes, since the evaluability criteria are different for the two sets of variables. A subject can be non-evaluable for partial data (e.g., birth outcomes only, all monthly gingivitis outcomes, or only specific monthly gingivitis outcomes). The criteria for evaluability are outlined in Section 5.6. There will be one population for Intent-to-Treat, which is defined as those subjects who were randomized and received study product

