5.6 Subject Evaluability Criteria for Randomized Subjects

5.6.1 Evaluability for Birth Outcomes

Subjects' birth outcome data (e.g. gestational age (GA), birth weight) will be assessed for evaluability based on the following criteria:

- 1) Drops: Declare as non-evaluable those subjects who were randomized and dropped from the study
- 2) Visit and Product Criterion
For purposes of evaluability, a *missed visit* occurred when an eligible subject (still pregnant) did not attend a visit.
 - a) Visit Criterion: Declare as non-evaluable those subjects who *missed 2 or 3* eligible post-baseline monthly visits.
 - b) Product Criterion (% of entire pregnancy with product): If the supply of products was less than 33.3% of the duration of the subject's entire pregnancy, then that subject will be non-evaluable.
- 3) Failed Entrance Criteria: Subjects who failed any entrance criteria at Baseline will be non-evaluable
 - Autoimmune disease
 - Type 2 Diabetes
 - > 24 weeks GA
 - < 30 bleeding sites
- 4) Failed Continuance Criteria: Subjects who had any of the following will be non-evaluable
 - Evidence/documentation of consistent non-compliance with assigned test product use (either from general comments or continuance criteria)
 - Elective termination of pregnancy
- 5) Pre-existing Condition: Subjects who had any of the following diseases/conditions or treatments that may impact GA will be non-evaluable
 - Uterine Abnormality (medically-significant)
 - Rh Incompatibility (untreated)
 - Previous Classical C-Section
 - Sickle Cell Disease
- 6) Adverse Event: Subject who had the following treatments that may impact GA will be non-evaluable

- Emergency C-Section with concomitant appendectomy due to stump appendicitis
- 7) Congenital Anomaly: Subjects who had the following medically significant congenital anomalies that may impact GA will be non-evaluable
- Trisomy 21
 - Fetal Hydrocephalus
 - Tetralogy of Fallot

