6.0. Statistical Methods and Determination of Sample Size

All statistical tests will be 2-sided tests except where noted; and any treatment difference p-values less than 0.05 will be cited as statistically significant. The analysis for the evaluable population will be considered as the primary population and the Intent-to-Treat (ITT) analyses will be considered secondary.

The primary test will be the treatment effect test for 3-month change from baseline for Löe-Silness. No adjustments for multiple testing will be employed.

All statistical tests will be carried out using SAS® version 9 (SAS Institute Inc., Cary, NC).

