- Women with no labor delay medication or procedures.
- By Age group (< median age vs. \geq median age)
- Pregnancy History (previous pregnancies (Y/N))

Additional analyses may also be performed in order to more fully understand the data.

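### Any randomised woman who is dropped leaves the primary birth-outcome analysis, although her delivery can be read from medical records without dental visits or product use.

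*Protocol*

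**What the plan says.** Protocol section 6 opens its list with "Subjects may be excluded from the study or the analysis due to". The grounds include non-compliance, use of other oral hygiene products, "antibiotic, systemic corticosteroid or immunosuppressive therapy", urgent dental treatment, and any condition the investigator thinks could interfere with safe completion. One list serves both the dental and the maternity objective.

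For birth outcomes, SAP 5.6.1 item 1 reads "Declare as non-evaluable those subjects who were randomized and dropped from the study". It makes no distinction by reason. Item 4 of the same section is narrower: the only continuance failures it names are consistent non-compliance and elective termination. Item 2 removes women who missed two or three monthly visits or whose product supply covered too little of the pregnancy.

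SAP 6.0 sets the hierarchy for all endpoints: "The analysis for the evaluable population will be considered as the primary population and the Intent-to-Treat (ITT) analyses will be considered secondary". SAP 5.5 defines the other set: "There will be one population for Intent-to-Treat, which is defined as those subjects who were randomized and received study product".

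On the source of the outcome, Protocol section 15 (Maternity Variables) says that "pertinent medical records are reviewed after delivery to determine maternity outcomes relating to gestational age". Section 3 (Maternity Outcome) has blinded staff abstract these data separately. For drop-outs, that section mentions an accountability form, and Appendix 1 (Case Report Forms) adds "All data gathered on the subject prior to discontinuation will be made available to the Sponsor". Neither says whether delivery is still abstracted after a drop.

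**The concern.** The continuance grounds have an obvious purpose for a gingivitis score, which needs a dental visit and can be disturbed by other treatment. Gestational age and birth weight need neither a visit nor continued product use, so removing a woman's delivery because she left the dental part discards an outcome that could be known.

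The removal happens after randomisation and on judgement. Some grounds (illness, drug therapy) may be related to the course of the pregnancy. Others (non-compliance) may differ by arm, since the regimen asks more of women than the control does. Either way, the arms compared in the primary maternity analysis need no longer be the arms that were randomised.

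Gestational age is the secondary variable that the SAP calls most important, and it set the sample size, so the composition of its analysis set deserves care.

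**Working it through.** **1. The plan's own figure.** Protocol section 11: 300 per group, variability 4.1 (taken as an SD in weeks), two-sided alpha 0.05, 90% power, difference about 1.1 weeks.
- Detectable difference = (1.960 + 1.282) × 4.1 × √(2/300) = 1.085, which rounds to 1.1.
- Power at 1.1 weeks is 0.908; 292 per group would give 90%. The figure reproduces, so 1.1 weeks is the yardstick below.

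**2. The chain in the text.**
- Protocol 6 permits the drop, at discretion.
- SAP 5.6.1 item 1 converts any drop into exclusion from the evaluable birth-outcome set.
- SAP 6.0 makes that set primary.
- Protocol sections 3 and 15 show that the outcome comes from records.
- SAP 5.6.1 item 4 does not list drug therapy or illness, but item 1 brings these grounds back whenever they lead to a drop. Items 1 and 4 and Protocol 6 therefore do not describe one consistent rule for birth outcomes.

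**3. What the interim shows (SAP section 3).**
- ITT 188, evaluable 163: 188 − 163 = 25, and 25/188 = 13.3% outside the evaluable set, for all reasons and under a different evaluability rule from the final one. The share due to drops is not given.
- SD implied by the gestational age table = difference/(1.960 + 0.842) × √(n/2). At 1.143 weeks this gives 1.143/2.802 × √(246/2) ≈ 4.52 (evaluable) and 1.143/2.802 × √(232/2) ≈ 4.39 (ITT). The slightly larger evaluable SD neither shows nor rules out selective loss of early deliveries.

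**4. Possible size for mean gestational age (assumptions, not document figures).** Let retained women have equal means in both arms, let dropped women deliver g weeks earlier, and let p be the share dropped. The full-arm mean is then lower than the retained mean by p × g, so the difference hidden is (p_control − p_regimen) × g.

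| p control v regimen | g = 2 | g = 4 | g = 6 |
|---|---|---|---|
| 2% v 1% | 0.02 | 0.04 | 0.06 |
| 5% v 2.5% | 0.05 | 0.10 | 0.15 |
| 10% v 5% | 0.10 | 0.20 | 0.30 |
| 5% v 5% | 0 | 0 | 0 |

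If the imbalance runs the other way, the sign reverses. With equal shares (5% v 5%) the difference is unbiased, and each arm mean is raised by 0.05 × g, or 0.10 to 0.30 weeks.

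**5. Preterm birth.** SAP 6.4 tests this by logistic regression. If a share q of women heading for preterm delivery is dropped, the odds p/(1 − p), with p now the true preterm rate, become p(1 − q)/(1 − p). With assumed true rates of 15% (control) and 10% (regimen):
- Equal q in both arms: the odds ratio stays at (0.15/0.85)/(0.10/0.90) = 1.59 for every q. What is lost is events, and so power.
- Unequal q: the ratio is multiplied by (1 − q_control)/(1 − q_regimen). For 30% v 10% it is 1.59 × 0.70/0.90 = 1.24; for 10% v 30% it is 1.59 × 0.90/0.70 = 2.04. These shares are illustrative and large.

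**The case against.** The other side has good points, and most of them limit how far the concern goes.

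- Protocol 6 is permissive, and no passage says that any woman was dropped for drug therapy. Continuance is scheduled only at Months 1 to 3. With entry at 8 to 24 weeks, the last check falls at about 20 to 37 weeks, so later events meet no scheduled check. This stands; the point concerns only women actually dropped.
- A reader might infer that antibiotics and corticosteroids mark threatened early labour, so that the rule selectively removes early deliveries. The documents do not say so. SAP 6.4 foresees a subgroup, "Women with no labor delay medication or procedures", but names neither drug class.
- A reader might infer that dropped women's deliveries are never collected, so that ITT cannot recover them. That reads too much into silence. Section 15 calls for record review for each subject, the Appendix 1 sentence does not forbid later abstraction, and at the interim about 184 women had delivery data against 163 evaluable. Whether any of the difference were drops is not stated.
- ITT is already planned, and gestational age is secondary to Month 3 Löe-Silness. This lowers the severity. It does not remove the problem, because ITT is placed second and its completeness after a drop is left unstated.

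**Conclusion.** The concern holds for the primary maternity analysis: following the plan removes randomised women whose outcome is knowable, on grounds that may relate to the pregnancy or to the arm. The conclusion rests on the text, not on a wrong figure. The size and direction of bias cannot be computed from the documents. In the mean gestational age illustrations the hidden difference is at most 0.30 weeks of the 1.1-week design difference, and nil when drop shares and delivery gaps are equal.

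Two larger numbers are tempting and should not be used:
- **20% lost, from 600 evaluable of 750.** Protocol 11 and SAP 6.8 give three reasons for the extra 150 women, and replacing non-evaluable women is only one.
- **A 5-point preterm effect cut by 8%, 24% or 43%.** These figures follow from p(1 − q)/(1 − pq) with the same assumed 15% v 10% rates and q of 10%, 30% or 50% in both arms. They are risk differences under assumed shares; the odds ratio that the SAP tests does not move.

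This is a low-cost improvement of moderate severity, not a condition for the trial's primary conclusion.

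**What to change.** - **Follow-up.** State in the protocol that a drop or continuance failure does not end maternity record abstraction. Abstract delivery for every randomised woman unless she withdraws consent to record access.
- **Analysis set.** Delete SAP 5.6.1 item 1 as a ground for removing a known delivery. Make ITT (randomised, received product, delivery known) primary for birth outcomes and the evaluable set supportive. Changing item 1 alone would do little, because the missed-visit and product-supply rules in item 2 would remove many of the same women.
- **Reporting.** Tabulate drops by reason and arm, with the number in each cell whose delivery is known.
- **Consistency.** Reconcile Protocol 6 with SAP 5.6.1 items 1 and 4 as to what they mean for birth outcomes. No clinical continuance rule needs to change, and the gingivitis rules are untouched.

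The cost is a wording change to both documents, made before the blind is broken, and some additional record abstraction by staff already doing that work. The downside is that some retained women will have had little product exposure, so the primary estimate describes assignment to the regimen rather than full use; the supportive evaluable analysis addresses the latter.
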